5.3. Lifestyle Considerations

Not applicable.

5.4. Screen Failures

Screen failure is defined as participants who consent to participate in the clinical study but are not subsequently randomly assigned to study intervention. A minimal set of screen failure information is required to ensure transparent reporting of screen failure participants to meet the

Consolidated Standards of Reporting Trials (CONSORT) publishing requirements and to respond to queries from regulatory authorities. Minimal information includes demography, screen failure details, eligibility criteria, and any serious adverse event (SAE).

5.4.1. Allowed Retesting of Screening Investigations

Repeating laboratory tests during the screening period does not constitute rescreening.

In particular, the following laboratory tests may be repeated once during the screening period to determine a participant's eligibility for randomization:

- tests for ANA, CCI [REDACTED]
- tests related to lupus nephritis, and
- clinical chemistry, hematology, calculation of estimated glomerular filtration rate.

See Section 8.2.6 for retesting related to TB.

5.4.2. Rescreening of Individuals Who Failed Screening

Informed consent for rescreenings

Individuals who are to be rescreened must first sign a new ICF (Appendix 10.1, Section 10.1.3). Such individuals will be assigned a new participant number.

Rescreening after failure to meet study entry criteria

An individual who does not meet the criteria for participation in this study may be rescreened **one time** if the reason for the screen failure has resolved and if the sponsor has approved the rescreening. The interval between the failure to meet study entry criteria and the start of rescreening should be at least 4 weeks.

Rescreening for administrative reasons

An individual may be rescreened **one time** for an administrative reason, including, for example, but not limited to, falling out of the screening window because of scheduling conflicts. The sponsor does not need to approve rescreening for an administrative reason. The rescreening can start immediately after the administrative reason has resolved.

Procedures not required to be repeated during rescreening

Individuals in rescreening who have already completed the protocol-required screening chest x-ray (CXR) or TB tests are not required to repeat these procedures if they were performed within 90 days before the date of signing the rescreening ICF. However, these procedures can be repeated at the discretion of the investigator.

6. Study Intervention

Study intervention is defined as any investigational intervention, marketed product, placebo, or medical device intended to be administered to a study participant according to the study protocol.

6.1. Study Interventions Administered

Study interventions

This study involves 3 dose levels of LY3471851 and placebo, as shown.

Treatment Name	LY3471851	Placebo
Dosage Formulation	CCI	0.9% sodium chloride
Dosage Levels		not applicable
Routes of Administration	subcutaneous injection	subcutaneous injection
Dosing Instructions	Dosing every 2 weeks	Dosing every 2 weeks

LY3471851 drug product will be provided as a sterile solution in a vial for SC injection. The drug product vials will be supplied in cartons, with the appropriate quantity specific to the planned dispensing schedule of the investigation product (IPs). Dosing solutions will be prepared at each clinical study site by an unblinded pharmacist (or other unblinded qualified individual) and loaded into syringes for SC dosing (see Section 6.3 on blinding). When the dosing solutions are prepared according to the provided instructions, it will not be possible to distinguish LY3471851 from placebo.

Monitoring after dose administration

All participants should be monitored for 30 minutes or longer after dosing, according to investigator practice or local standard of care.

Packaging and labeling

LY3471851 will be supplied by the sponsor or its designee in accordance with current Good Manufacturing Practice (cGMP). Clinical trial materials will be labeled according to the country's regulatory requirements. All IPs will be stored, inventoried, reconciled, and destroyed according to applicable regulations.

6.2. Preparation/Handling/Storage/Accountability

The Pharmacy Manual provides instructions for the preparation, handling and storage of LY3471851 drug product and placebo, and site responsibility and accountability for the administered products.

Investigators should consult the information provided in the Pharmacy Manual or the label for specific preparation and administration information, including warnings, precautions, contraindications, adverse reactions, and dose modifications.

Preparation

The IPs must be prepared by an unblinded pharmacist (or other unblinded qualified individual) who is not involved in any other study-related procedures.

Handling and storage

Follow the storage and handling instructions for the IP as noted in the IP packaging. The handling and storage information for the administered product is located in the Pharmacy Manual.

Site responsibilities and accountability

The following are responsibilities of the investigator or his or her designee:

- The investigator or designee must confirm appropriate temperature conditions have been maintained during transit for all study intervention received and that any discrepancies are reported and resolved before use of the study intervention.
- Only participants enrolled in the study may receive study intervention, and only authorized site staff may supply or administer study intervention. All study intervention must be stored in a secure, environmentally controlled, and monitored (manual or automated) area in accordance with the labeled storage conditions with access limited to the investigator and authorized site staff.
- The investigator, institution, or the head of the medical institution (where applicable) is responsible for study intervention accountability, reconciliation, and record maintenance (that is, receipt, reconciliation, and final disposition records).

Further guidance and information for the final disposition of unused study interventions are provided in the Pharmacy Manual.

The investigator or designee is also responsible for

- explaining the correct use of the study interventions
- verifying that instructions are followed properly
- maintaining accurate records of IP dispensing and collection, and
- returning all unused medication to Lilly or its designee at the end of the study.

Note: In some cases, sites may destroy the material if, during the investigative site selection, the evaluator has verified and documented that the site has appropriate facilities and written procedures to dispose of clinical materials.

6.3. Measures to Minimize Bias: Randomization and Blinding

Blinding will be maintained throughout the conduct of the study as described in the separate Unblinding Plan.

Method of treatment assignment

Assignment to treatment groups will be determined by a computer-generated random sequence using an interactive web-response system (IWRS).

Unblinded pharmacist

Investigators and all individuals involved in administering the blinded treatment or performing assessments will remain blinded to each participant's assigned study intervention throughout the course of the study. To maintain this blind, an otherwise uninvolved party (unblinded pharmacist or other unblinded qualified individual) will be responsible for the preparation and dispensation of all study intervention. Blinded site personnel will administer the study intervention to the participant.

Independent assessor for injection site reactions

At every visit following the first dose and prior to any blinded study activity, an independent Injection Site Reaction (ISR) assessor who is not involved with other study procedures will evaluate each participant for the presence of ISRs. If the participant presents with symptoms of an ISR (see Section 8.2.11), the ISR assessor will examine the impacted areas and record the information in the electronic case report form (eCRF).

Whether an ISR is present or not, the ISR assessor will use a bandage (or similar material) to cover the anatomical area where the participant received his or her last dose. The purpose of covering this area is to minimize bias when blinded study personnel conduct other study assessments, given the known frequency of ISRs with the molecule.

Emergency unblinding

Emergency unblinding for adverse events may be performed through the IWRS. This option may be used ONLY if the participant's well-being requires knowledge of the participant's treatment assignment. All actions resulting in an unblinding event are recorded and reported by the IWRS.

If a participant's study treatment assignment is unblinded to blinded site personnel performing assessments, including the investigator, or to the participant, the participant must be discontinued from study drug, unless the investigator obtains specific approval from the sponsor's medical monitor for the participant to continue (Section 7.1.1).

In case of an emergency, the investigator has the sole responsibility for determining if unblinding of a participant's intervention assignment is warranted. Participant safety must always be the first consideration in making such a determination. If the investigator decides that unblinding is warranted, it is the responsibility of the investigator to promptly document the decision and rationale and notify the sponsor as soon as possible.

In cases where there are ethical reasons to have the participant remain in the study, the investigator must obtain specific approval from the sponsor's clinical research physician for the participant to continue in the study.

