Hepatitis C virus (HCV) screening tests		X	HCV RNA will be measured to confirm positive hepatitis C virus antibody (Section 8.2.8).
Hepatitis B virus (HBV) screening tests		X	Includes testing for HBsAg and anti-HBc.
HBV DNA		X	Only for participants who are positive for anti-HBc at screening (Section 8.2.7).
Total immunoglobulins (IgG)		X	

Prescreening and screening periods of Study J1P-MC-KFAJ			
Visit 1 procedures may be conducted over more than 1 day as long as all activities are completed within the allowable visit tolerance.			
	Prescreening (optional)	Screening (required)	Comment
Visit number	V601	V1	
Weeks from randomization		-5	
Study day		—	
Visit interval tolerance (days)		-35 to -3	
Fasting visit			No fasting in this period.
CCI [REDACTED]	■	■	
[REDACTED]	■	■	
[REDACTED]	■	■	

Abbreviations: CCI [REDACTED]; C-SSRS = Columbia–Suicide Severity Rating Scale; DNA = deoxyribonucleic acid; ECG = electrocardiogram; HBsAg = hepatitis B surface antigen; HIV = human immunodeficiency virus; ICF = informed consent form; RNA = ribonucleic acid; CCI [REDACTED]; SF = short form; SLE = systemic lupus erythematosus; SLEDAI-2K = Systemic Lupus Erythematosus Disease Activity Index 2000; V = visit.

Treatment period of Study J1P-MC-KFAJ																
For early terminations that occur before the last visit in treatment period, see the activities listed for ETV in this table.																
Visit number	V2	V3	V4	V5	V6	V7	V8	V9	V10	V11	V12	V13	V14	V15	ETV	Comment
Weeks from Randomization	—	1	2	4	6	8	10	12	14	16	18	20	22	24	—	
Study day	1	8	15	29	43	57	71	85	99	113	127	141	155	169	—	
Visit interval tolerance (days)	—	±3	±3	±3	±3	±3	±3	±3	±3	±3	±3	±3	±3	±3	—	
Fasting visit	X							X						X		
Inclusion and exclusion criteria, review and confirm	X															Participant eligibility must be reviewed and confirmed by an eligibility review committee prior to randomization.
Concomitant medications	X	X	X	X	X	X	X	X	X	X	X	X	X	X	X	
Adverse events (AEs)	X	X	X	X	X	X	X	X	X	X	X	X	X	X	X	CCI [REDACTED]
Physical Evaluation																
Height	X															Without shoes.
Weight	X			X		X		X		X		X		X	X	
Vital signs	X	X	X	X	X	X	X	X	X	X	X	X	X	X	X	Blood pressure, body temperature, pulse rate. Vital signs should be measured after participant has been sitting for at least 5 minutes.
Injection site assessment		X	X	X	X	X	X	X	X	X	X	X	X	X	X	Performed by independent injection site assessor before participant is seen by blinded site staff (Section 6.3, Section 8.2.11).

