Treatment period of Study J1P-MC-KFAJ																
For early terminations that occur before the last visit in treatment period, see the activities listed for ETV in this table.																
Visit number	V2	V3	V4	V5	V6	V7	V8	V9	V10	V11	V12	V13	V14	V15	ETV	Comment
Weeks from Randomization	—	1	2	4	6	8	10	12	14	16	18	20	22	24	—	
Study day	1	8	15	29	43	57	71	85	99	113	127	141	155	169	—	
Visit interval tolerance (days)	—	±3	±3	±3	±3	±3	±3	±3	±3	±3	±3	±3	±3	±3	—	
Fasting visit	X							X						X		
Symptom-directed physical examination				X		X		X		X		X		X	X	See Section 8.2.2. The SLE symptom physical assessment is captured in the electronic tablet.
12-lead ECG (local)								X						X	X	
Patient-Reported Outcomes (Electronic)																

QIDS-SR16	X	X	X	X	X	X	X	X	X	X	X	X	X	X	X	X	Administer before any clinical assessments.
-----------	---	---	---	---	---	---	---	---	---	---	---	---	---	---	---	---	---------------------------------------------

Treatment period of Study J1P-MC-KFAJ																
For early terminations that occur before the last visit in treatment period, see the activities listed for ETV in this table.																
Visit number	V2	V3	V4	V5	V6	V7	V8	V9	V10	V11	V12	V13	V14	V15	ETV	Comment
Weeks from Randomization	—	1	2	4	6	8	10	12	14	16	18	20	22	24	—	
Study day	1	8	15	29	43	57	71	85	99	113	127	141	155	169	—	
Visit interval tolerance (days)	—	±3	±3	±3	±3	±3	±3	±3	±3	±3	±3	±3	±3	±3	—	
Fasting visit	X							X						X		

Clinician-Administered Questionnaires (Electronic)																
BILAG 2004	X			X		X		X		X		X		X	X	Collected via an electronic tablet device.

[figure not shown]
Physician’s Global Assessment (PGA) of Disease Activity – VAS	X			X		X		X		X		X		X	X	Collected via an electronic tablet device.
SLEDAI Flare Index	X			X		X		X		X		X		X	X	Collected via an electronic tablet device.
SLEDAI-2K	X			X		X		X		X		X		X	X	Collected via an electronic tablet device.

Clinician-Administered Questionnaires (Paper)																
C-SSRS Since Last Visit	X	X	X	X	X	X	X	X	X	X	X	X	X	X	X	Adapted for the assessment of ideation and behavior categories only.

Treatment period of Study J1P-MC-KFAJ																
For early terminations that occur before the last visit in treatment period, see the activities listed for ETV in this table.																
Visit number	V2	V3	V4	V5	V6	V7	V8	V9	V10	V11	V12	V13	V14	V15	ETV	Comment
Weeks from Randomization	—	1	2	4	6	8	10	12	14	16	18	20	22	24	—	
Study day	1	8	15	29	43	57	71	85	99	113	127	141	155	169	—	

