Visit interval tolerance (days)	—	±3	±3	±3	±3	±3	±3	±3	±3	±3	±3	±3	±3	±3	—	
Fasting visit	X							X						X		
Self-Harm Supplement Form	X	X	X	X	X	X	X	X	X	X	X	X	X	X	X	
Self-Harm Follow-Up Form	X	X	X	X	X	X	X	X	X	X	X	X	X	X	X	Required if triggered by the Self-Harm Supplement Form per instructions.
Laboratory Tests and Sample Collections																
Hematology	X	X	X	X	X	X	X	X		X		X		X	X	
Clinical chemistry	X	X	X	X	X	X	X	X		X		X		X	X	
Lipid panel	X							X						X	X	For the fasting lipid panel, participants should not eat or drink anything but water for 12 hours before the visit. Fasting is not required at an ETV. If a participant attends these visits in a nonfasting state, the sample should still be collected. This will not be considered a protocol violation.
Urinalysis	X			X		X		X		X		X		X	X	
Urine total protein, urine creatinine, and urine protein/urine creatinine ratio (calculation)	X			X		X		X		X		X		X	X	

Treatment period of Study J1P-MC-KFAJ																
For early terminations that occur before the last visit in treatment period, see the activities listed for ETV in this table.																
Visit number	V2	V3	V4	V5	V6	V7	V8	V9	V10	V11	V12	V13	V14	V15	ETV	Comment
Weeks from Randomization	—	1	2	4	6	8	10	12	14	16	18	20	22	24	—	
Study day	1	8	15	29	43	57	71	85	99	113	127	141	155	169	—	
Visit interval tolerance (days)	—	±3	±3	±3	±3	±3	±3	±3	±3	±3	±3	±3	±3	±3	—	
Fasting visit	X							X						X		
Urine pregnancy (local)	X		X	X	X	X	X	X	X	X	X	X	X	X	X	Only for women of childbearing potential (Section 8.2.5.1 and Appendix 10.4) and women with a history of tubal ligation.
HBV DNA								X						X	X	Only for participants who are positive for anti-HBc at screening (Section 8.2.7).

Treatment period of Study J1P-MC-KFAJ																
For early terminations that occur before the last visit in treatment period, see the activities listed for ETV in this table.																
Visit number	V2	V3	V4	V5	V6	V7	V8	V9	V10	V11	V12	V13	V14	V15	ETV	Comment
Weeks from Randomization	—	1	2	4	6	8	10	12	14	16	18	20	22	24	—	
Study day	1	8	15	29	43	57	71	85	99	113	127	141	155	169	—	
Visit interval tolerance (days)	—	±3	±3	±3	±3	±3	±3	±3	±3	±3	±3	±3	±3	±3	—	

Randomization and Dosing																
Randomization	X															
Dosing	X		X	X	X	X	X	X	X	X	X	X	X			No dosing at V3 or V15

Abbreviations: ACR = American College of Rheumatology; [CCI] [REDACTED]
[REDACTED]
[REDACTED] BILAG
= British Isles Lupus Assessment Group; [CCI] [REDACTED] C-SSRS = Columbia–Suicide Severity

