6.19.4. Injection Site Reaction

At every visit following the first dose and prior to any blinded study activity, an independent ISR assessor who is not involved with other study procedures will evaluate each participant for the presence of ISRs between the visits.

The number and percentage of patients who experienced an ISR will be summarized by treatment group and by visit. The number and percentage of patients with the following ISR records will be summarized by treatment group and by visit. Details about ISR records are referred to the case report form.

- anatomical location of the injection site reaction
- abdomen side
- directionality of the anatomical location of the administration
- arm side
- thigh side
- whether the subject have any injection site erythema (reddening) or not
- severity of the injection site erythema
- whether the subject have any injection site induration (hardening or thickening of tissue) or not
- severity of the injection site induration
- whether the subject have any injection site pain (including burning) or not

- severity of the injection site pain
- whether the subject have any injection site pruritus
- severity of the injection site pruritus
- whether the subject have any injection site edema (swelling or accumulation of fluid in tissues at height above normal skin) or not
- severity of the injection site edema, and
- when did the injection related event occur, in relationship to the study treatment.

The frequency of the maximum severity of ISRs will be summarized by treatment group.

CCI

It will not be considered a protocol violation if the planned sample size is not achieved due to an insufficient number of consenting and eligible participants.

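### The blinding bandage has to cover only the area of the last dose, so an area dosed about 28 days before each efficacy rating may be visible to the blinded rater

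*Protocol*

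**What the plan says.** **Covering rule.** Under Protocol 6.3 an ISR assessor with no other study role sees the participant at each visit after the first dose. With or without a reaction, the assessor uses a bandage to "cover the anatomical area where the participant received his or her last dose". The stated purpose is to "minimize bias when blinded study personnel conduct other study assessments, given the known frequency of ISRs with the molecule". The Schedule of Activities (SoA, Protocol 1.3) fixes the order: "Performed by independent injection site assessor before participant is seen by blinded site staff".

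**Dosing and rating.** Protocol 6.1 gives "Dosing every 2 weeks", and the SoA adds "No dosing at V3 or V15". That makes 12 dosing visits, at Weeks 0, 2, ..., 22. The SoA places SLEDAI-2K, BILAG-2004 and PGA at Weeks 0, 4, 8, 12, 16, 20 and 24, and at early termination.

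**Skin.** Rash is a SLEDAI-2K item (Protocol 10.7.4). Active rash is one of two features that can satisfy inclusion criterion 7. Protocol 8.2.2, for the complete examination, leaves out only bandaged skin. Protocol 8.2.11 lists erythema and induration among ISR symptoms.

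**Location.** SAP 6.19.4 summarises the "anatomical location of the injection site reaction", with side fields for abdomen, arm and thigh.

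**Not stated.** Neither document says how long reactions last, how often they occur by arm, whether injection areas rotate, how long a bandage stays on, or that areas of earlier doses are to be covered.

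**The concern.** The masking step is tied to the most recent dose, but the interval between ratings is twice the dosing interval. A safeguard written to protect the rating therefore protects against only one of the two doses given since the rater last scored the participant.

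The primary endpoint is a drop of at least 4 points in a clinician-rated score. BICLA, SRI-4 and LLDAS are built from the same ratings. A visible older reaction could act in two ways:

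- The rater may suspect active drug, and the suspicion may colour judgement items and the PGA.
- The rater may take the mark for lupus rash and score it, which would count against response in that participant.

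These can pull in opposite directions.

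**Working it through.** The plan gives no figure on this point, so the check is a reading of the schedule.

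**Which dose is the last one when the bandage goes on.** The assessor works before any blinded activity, and blinded staff give the injection (Protocol 6.3). On a day with both a rating and a dose, covering therefore precedes that day's dose, and the covered area is that of the visit two weeks before. At Week 24 there is no dose, so the covered area is that of Week 22.

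**Age of each dose at rating** = 7 × (rating week − dose week).

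| Rating | Doses since previous rating | Must be covered (age) | Need not be covered (age) |
|---|---|---|---|
| Week 4 | 0, 2 | Week 2 (14 days) | Week 0 (28 days) |
| Week 8 | 4, 6 | Week 6 (14 days) | Week 4 (28 days) |
| Week 12 | 8, 10 | Week 10 (14 days) | Week 8 (28 days) |
| Week 16 | 12, 14 | Week 14 (14 days) | Week 12 (28 days) |
| Week 20 | 16, 18 | Week 18 (14 days) | Week 16 (28 days) |
| Week 24 | 20, 22 | Week 22 (14 days) | Week 20 (28 days) |

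**Visit windows.** Visits after Week 0 may each move by 3 days, so the uncovered dose is 28 ± 6 = 22 to 34 days old. At Week 4 the range is 28 ± 3 = 25 to 31 days, because the first dose has no window.

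**From schedule to consequence.** The gap matters only if all of these hold:

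1. The two doses went to different anatomical areas. No rotation rule is visible.
2. A reaction can still be seen at about four weeks. No duration is given.
3. The rater looks at that skin. This is plausible, since rash is scored.
4. For suspicion to be informative, such marks must be more frequent on active drug. No rates by arm are given.

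**How much hangs on item 4 (assumed rates, illustration only).** With 1:1:1:1 randomization, active to placebo is 3:1, so the chance of active drug before anything is seen is 75%. If a fraction q of active and r of placebo participants show a mark, the chance of active drug given a mark is 3q / (3q + r).

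- q = r: 75%, so the mark tells nothing.
- q = 0.30, r = 0.10: 0.90 / 1.00 = 90%.
- q = 0.30, r = 0.02: 0.90 / 0.92 = 98%.

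No bias estimate follows. Bias would be the share of participants affected times the shift in their scoring, and the documents give neither factor, nor the sign of the second.

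**The case against.** **Duration.** Nothing shows that reactions last four weeks, and Protocol 2.3 calls them mainly low grade. A reader might infer from the 14-day bandage that reactions last at least that long. That does not follow: the same rule applies at Week 1 and to participants without a reaction, so it is a blanket precaution. This stands. But the rule also applies at Visit 801 (day 211), 211 − 155 = 56 days after the Week 22 dose (day 155), where no efficacy rating is scheduled. A defence based on duration would have to explain why an area 28 days old may stay open at the visits that carry the primary endpoint.

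**Anatomical area.** The bandage covers an area, not a puncture point. If doses are repeated in one area, the older site may already be covered. The location fields in SAP 6.19.4 show where a reaction can be recorded, not that sites rotate. This stands, and it makes the point conditional.

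**Other documents.** The Unblinding Plan and Pharmacy Manual were not available and may contain covering or site-selection rules. This also stands.

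**Protocol 7.1.1** asserts that the presence or absence of a clinically significant ISR does not unblind. It gives no support, and it does not answer the reason that 6.3 itself offers for covering, "given the known frequency of ISRs with the molecule". Placebo is also injected, so a mark can at most suggest active drug.

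**Leakage by report.** Under Protocol 8.2.11 a participant can volunteer symptoms, and the investigator can record an ISR as an adverse event. The bandage was never a full seal, which limits what a wider bandage can gain.

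**A stronger reading** would be that the current rule biases SLEDAI-2K and PGA in favour of LY3471851, or exposes some stated share of active participants. The documents support neither. No share can be derived, and marks mistaken for rash could work against the drug.

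**Conclusion.** The gap in the covering rule is real on the face of the documents and is present at all six post-baseline ratings, Week 4 included. At each, the area dosed nominally 28 days earlier need not be covered. Its consequence is a possibility and not a demonstrated bias: it requires different areas for the two doses and a reaction still visible at 22 to 34 days. The size and direction of any effect on SLEDAI-4 response are unknown. This is a cheap improvement to an existing and sensible safeguard, not a flaw that undermines the primary analysis.

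**What to change.** Amend Protocol 6.3 so that, at every visit with an efficacy rating (early termination included), the ISR assessor covers each anatomical area dosed since the previous efficacy rating. This applies to all participants, whether or not a reaction is present. At other visits the present rule can stand. The assessor needs to know where the last two doses were given, so the injection area should be recorded at each dose. Check that the Unblinding Plan carries the same rule.

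Do not add bandages only where a reaction is visible. Only participants with a reaction would wear them, so the bandage itself would reveal what it is meant to hide.

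**Cost.** At most one more bandage per rating visit, placed by an assessor who is already there, and none if both doses went to the same area. The downside is slightly more skin hidden from rash scoring. Applying the rule to every participant keeps that loss independent of whether a reaction occurred. The change does not close the route through reported reactions in Protocol 8.2.11.
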